#### Safety Endpoints:

- TEAEs and SAEs
- Clinical laboratory tests, physical examination findings, vital signs and ECGs

### 5.3. Part C Endpoints

#### Primary Endpoint:

- Change from baseline to 48 Weeks in cerebral blood flow as measured by the TAMM TCD velocity

#### Secondary Endpoints:

- Change from baseline to Weeks 24 and 48 in Hb, LDH, indirect bilirubin and reticulocyte count
- Change from baseline to 24 weeks in cerebral blood flow as measured by the TAMM TCD velocity
- GBT440 PK ( $C_{max}$ ,  $AUC_{0-last}$ ,  $AUC_{0-inf}$ ,  $AUC_{0-24}$ ,  $T_{1/2}$ , accumulation ratio, blood/plasma ratio, RBC/plasma ratio, if appropriate) and percent Hb occupancy

#### Safety Endpoints:

- TEAEs and SAEs
- Clinical laboratory tests, physical examination findings, vital signs and ECGs

## 6. GENERAL CONSIDERATIONS FOR DATA ANALYSES AND HANDLING

### 6.1. Sample Size Considerations

**Part A:** A cohort size of up to approximately 6 participants for each age group: 6 to 11 and 12 to 17 is based on a typical size for a single-dose PK study and is intended to balance the desire to minimize exposure of pediatric participants to a novel compound at this stage of GBT440's development with the need to obtain PK, safety and tolerability data. No formal power or sample size calculations were performed to determine the cohort size.

**Part B:** Approximately 12 participants at 900 mg were selected to determine preliminary safety, tolerability, PK, laboratory effects and treatment response of GBT440 in pediatric participants with SCD. The number of participants may be increased to approximately 36 to further characterize the effect of multiple doses of GBT440. Upon a favorable review by the DSMB, dosing of a minimum of 6 participants at 1500 mg may commence (dependent on how many participants were enrolled at 900 mg, i.e. not to exceed a total study size of approximately 36).

For the endpoint of change from baseline to Week 24 in Hb, power calculations assume normally distributed data, a mean treatment effect (change from baseline) of 0.8 g/dL, with a standard deviation (SD) of 0.6 g/dL. For a two-sided alpha = 0.05 and N = 12, power exceeds 90% with a paired t-test to reject the null hypothesis of equality of post-treatment and baseline Hb means. The estimates of 0.8 g/dL and 0.6 g/dL for the mean and SD, respectively, are based on available Day 90 data from Cohorts 16 and (partial data) 17 from the GBT440-001 study.

**Part C:** Up to 50 pediatric participants who are 4 to 17 years of age with SCD will be enrolled. For the primary efficacy endpoint, change from baseline in TAMM TCD velocity at Week 48, a sample size of 30 participants achieves greater than 95% power to detect a mean difference of 15 cm/sec with an estimated sample standard deviation of 22 cm/sec using a paired t-test (two-sided) with a significance level (alpha) of 0.10.

## 6.2. Handling of Data

### 6.2.1. Visit Windows

Visit windows will be defined for Part B PRO measures. PRO measures include ePRO Screening and ePRO SCDSM.

**Table 1: Nominal Analysis Visit Windows for PRO Measures**

Nominal Visit Time	Study Day Range for Statistical Analysis
Screening	[-28, -1]
Week 4	[1, 28]
Week 8	[29, 56]
Week 12	[57, 84]
Week 16	[85, 112]
Week 20	[113, 140]
Week 24	[141, 168]
Week 28	[169, 196]

Note: ePRO SCDSM is measured every day from the first day of screening to Week 28 post first dose. Participants must complete a minimum of 14 days during Screening.

### 6.2.2. Missing Start and Stop Dates for Prior and Concomitant Medication

For missing start day only: Day will be imputed as the first day of the month (i.e., 1) with the following exception: If the partial date falls in the same month and year as the treatment start date then the concomitant medication start date will be imputed as the treatment start date.

For missing start day and month: Day and month will be imputed as the first day of the year (i.e., 1 January) with the following exception: If the partial date falls in the same year as the treatment start date then the concomitant medication start date will be imputed as the treatment start date.

For missing stop day only: Day only will be imputed as the last day of the month (i.e., 28, 29, 30, or 31).

For missing stop day and month: Day and month will be imputed as the last day of the year (i.e., 31 December).

### **6.2.3. Missing Start and Stop Dates for Adverse Events**

For missing start day only: Day will be imputed as the first day of the month (i.e., 1) with the following exception: If the partial date falls in the same month and year as the treatment start date then the adverse event start date will be imputed as the day prior to the treatment start date.

For missing stop day only – Day only will be imputed as the last day of the month (i.e., 28, 29, 30, or 31).

## **7. ANALYSIS POPULATIONS**

### **7.1. Efficacy Evaluable Population**

All participants who received any amount of study drug will be included in the Efficacy Evaluable population (EE). All efficacy analyses will be based on the EE population.

### **7.2. Safety Population**

All participants who received any amount of study drug will be included in the Safety population. All safety analyses will be based on the Safety population. The Safety Population is defined as all subjects who receive at least one dose of study medication. This population will be used in the assessment and reporting of safety data.

### **7.3. PK Population**

All participants who receive any amount of study drug and who provide PK data from at least one post dose sample in plasma will be included in the PK population. Additional details are provided in a separate plan.

## **8. STATISTICAL METHODS**

The interim data analysis will be performed at the time of the database snapshot.

Statistical programming and analyses will be performed using SAS® Version 9.4 or higher.

Select Part A summaries will be presented for the 600 mg dose level by age group (6-11 years and 12-17 years) and Overall voxelotor (both age groups).

Part B summaries will be presented by dose level (900 mg and 1500 mg).

Continuous variables will be descriptively summarized using number of participants (n), mean, standard deviation (SD), median, minimum, maximum, and, as appropriate, geometric mean.

Categorical variables will be descriptively summarized by presenting the number (frequency) and percentage in each category.

## **8.1. Subject Disposition, Demographic and Baseline Characteristics**

### **8.1.1. Subjects Disposition**

Participant disposition will be presented in terms of the numbers and percentages of participants who completed the treatment and discontinued from treatment. The reasons for early treatment discontinuation will be presented. Similar results will be presented for subjects who discontinue study.

Screen failures along with the reasons for screen failure will be listed only.

### **8.1.2. Demographic and Baseline Characteristics**

The demographic variables collected in this study include age (years) at Screening, sex, race, and ethnicity and will be summarized descriptively. Height (cm), weight (kg) and BMI (kg/m^3) at Screening will be presented using descriptive statistics. Participants who record more than one race will be grouped into a single category denoted as multi-racial.

### **8.1.3. Baseline Sickle Cell Disease Characteristics**

Number of VOCs including the number of VOCs requiring hospitalization and the number of blood transfusion during the previous 12 months will be summarized categorically.

Additional summaries including the number and percentage of participants who currently use HU, who have each genotype (HbSS or HbSBO) and who experienced a sickle cell complication prior to study enrollment will be presented. Baseline lab values including Hb, HbF (Part B only), and reticulocyte count will be summarized using descriptive statistics.

In Part B, prior HU results including most recent labs prior to initiation of HU, maximum tolerated dose of HU and lab results one month post MTD of HU will be provided in a listing.

### **8.1.4. Other Medical History**

Other medical history will be summarized by System Organ Class (SOC) and Preferred Term (PT) according to Medical Dictionary for Regulatory Activities (MedDRA), version 20.0 coding dictionary.

## **8.2. Efficacy Analysis**

All efficacy data in Part B will be summarized using the EE population.

### **8.2.1. Analysis of the Primary Efficacy Endpoint**

Change from baseline in hemoglobin to Week 24 will be summarized descriptively. The changes from baseline will be presented including the (absolute) values at each visit. Additionally, a responder endpoint defined as an increase in Hb >1 g/dL compared to Baseline, will be summarized descriptively at Week 12 through Week 24. No imputation will be performed for this endpoint.

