10. DATA ANALYSIS AND STATISTICAL PLANS

10.1. Sample Size

Part A: A cohort size of up to approximately 6 participants for each age group: 6 to 11 and 12 to 17 is based on a typical size for a single-dose PK study and is intended to balance the desire to minimize exposure of pediatric participants to a novel compound at this stage of voxelotor's development with the need to obtain PK, safety and tolerability data. No formal power or sample size calculations were performed to determine the cohort size.

Part B: Approximately 12 participants at 900 mg were selected to determine preliminary safety, tolerability, PK, laboratory effects and treatment response of voxelotor in pediatric participants with SCD. The number of participants may be increased to approximately 36 to further characterize the effect of multiple doses of voxelotor. Upon a favorable review by the DSMB, dosing of a minimum of 6 participants at 1500 mg may commence (dependent on how many participants were enrolled at 900 mg, ie, not to exceed a total study size of approximately 36).

The study with $N = 12$ for 900 mg is adequately powered for the primary endpoint of change from baseline to Week 24 in Hb. Power calculations assume normally distributed data, a mean treatment effect (change from baseline) of 0.8 g/dL, with a standard deviation (SD) of 0.6 g/dL. For a 2-sided alpha = 0.05 and $N = 12$, power exceeds 90% with a paired t-test to reject the null hypothesis of equality of post-treatment and baseline Hb means. The estimates of 0.8 and 0.6 g/dL for the mean and SD, respectively, are based on available Day 90 data from Cohorts 16 and (partial data) 17 from the GBT440-001 study.

Part C: Up to 50 pediatric participants who are 4 to 17 years of age with SCD will be enrolled. For the primary efficacy endpoint, change from baseline in TAMM TCD velocity at Week 48, a sample size of 30 participants achieves greater than 95% power to detect a mean difference of 15 cm/sec with an estimated sample standard deviation of 22 cm/sec using a paired t-test (2-sided) with a significance level (alpha) of 0.10.

Part D: Approximately 30 pediatric participants with SCD who are 6 months to < 4 years of age will be enrolled. The sample size was selected to provide descriptive assessment of safety, tolerability, and PK effects of voxelotor in this younger age group with no formal statistical assumptions.

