### 5.2. Part B Endpoints

#### Primary Endpoint:

- Change from baseline to Week 24 in Hb

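### The power stated for the Part B primary endpoint rests on a paired t-test that no analysis section pre-specifies, and no confidence interval is planned in its place

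*SAP*

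**What the plan says.** The Part B primary objective is efficacy, judged by improvement in anemia (Part A/B SAP 3.2). The primary endpoint is "Change from baseline to Week 24 in Hb" (SAP 5.2).

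On sample size, protocol 10.1 says that 12 participants at 900 mg "is adequately powered for the primary endpoint of change from baseline to Week 24 in Hb". SAP 6.1 gives the assumptions as "a mean treatment effect (change from baseline) of 0.8 g/dL, with a standard deviation (SD) of 0.6 g/dL" and the result as "power exceeds 90% with a paired t-test to reject the null hypothesis of equality of post-treatment and baseline Hb means", at a two-sided alpha of 0.05. The synopsis carries the same calculation. It also says that the size was not chosen on statistical grounds but to give preliminary safety, PK and response information.

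On analysis, SAP 8.2.1 says "Change from baseline in hemoglobin to Week 24 will be summarized descriptively". SAP 8 gives the statistics: "Continuous variables will be descriptively summarized using number of participants (n), mean, standard deviation (SD), median, minimum, maximum, and, as appropriate, geometric mean". Part B results are shown by dose level. Protocol 10.3 and 10.3.3 likewise promise descriptive statistics for the primary endpoint and for hemoglobin. SAP 10, on changes to the planned analyses, mentions only the symptom-exacerbation endpoint.

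**The concern.** Power is the probability that a named test rejects a named null hypothesis. SAP 6.1 names both, and then neither the protocol's analysis sections nor the SAP's include the test. A reader who relies on the power claim will look for its counterpart in the results and find no planned one.

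The practical loss is precision. Part B is the only part with hemoglobin as its primary efficacy endpoint, and its results are split by dose. The power statement covers 900 mg only, while 1500 mg may have as few as 6 participants. Two mean changes printed side by side without intervals would look equally firm when they are not.

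**Working it through.** **Inputs.** Mean change 0.8 g/dL, SD 0.6 g/dL, two-sided alpha 0.05 and n=12 at 900 mg (SAP 6.1); minimum of 6 at 1500 mg (SAP 6.1); 25 at 900 mg and 7 at 1500 mg among the adolescents in the safety review described in protocol 3.5.2. I take 0.6 as the SD of the change, and I apply the same mean and SD to 1500 mg. The second step is my assumption, since the documents state these values for the 900 mg calculation only.

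**The plan's own figure.** Exact power of a paired t-test comes from the noncentral t distribution with n−1 degrees of freedom and noncentrality (0.8/0.6)×√n. At n=12 the noncentrality is 1.333×3.464 = 4.62 and the critical value is t(0.975, 11) = 2.201. Power is 98.7%, which agrees with the stated figure of more than 90%. The smallest n reaching 90% is 9. At n=12, power stays at or above 90% for an SD of the change up to about 0.78 g/dL.

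If 0.6 were instead the SD at each time point, power at n=12 would depend on the correlation between the two measurements: 84% at 0, 93% at 0.25 and 98.7% at 0.5. The stated figure would then fail only at low correlation.

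**Precision.** The half-width of a 95% confidence interval for the mean change is t(0.975, n−1)×0.6/√n. For example, at n=12 it is 2.201×0.6/3.464 = 0.38.

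| Dose | n | Source of n | Power | Half-width (g/dL) |
|---|---|---|---|---|
| 900 mg | 12 | planned minimum | 98.7% | 0.38 |
| 900 mg | 25 | protocol 3.5.2 | >99.9% | 0.25 |
| 1500 mg | 6 | planned minimum | 74.3% | 0.63 |
| 1500 mg | 7 | protocol 3.5.2 | 83.4% | 0.55 |

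At n=6 the half-width is 0.63/0.8, or about 79% of the assumed effect. With the group sizes in protocol 3.5.2, the 1500 mg interval is about 0.55/0.25 = 2.2 times as wide as the 900 mg interval. Those are counts of participants enrolled. Missing values are not imputed, so the number with a Week 24 hemoglobin can only be equal or smaller.

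**Sample-size text against analysis text.** The paired t-test appears in protocol 10.1, the synopsis and SAP 6.1. It does not appear in protocol 10.3 or 10.3.3, SAP 8 or 8.2.1, or the Part B table list in SAP 11.3. No confidence interval for the primary endpoint appears in any of these places.

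**The case against.** The strongest reply is that this is an open-label Phase 2a study in which descriptive analysis is legitimate, and that the documents are more consistent than they first appear. Several stronger readings are tempting and are not supported.

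- *That the t-test determined the sample size.* The synopsis denies a statistical basis, and both protocol 10.1 and SAP 6.1 say about 12 participants were chosen for preliminary safety, PK and response. The power figure reads as a check on a number chosen for other reasons. That leaves the synopsis in tension with the adequacy statement in protocol 10.1.
- *That the SAP removed a planned test.* SAP 2 does supersede the protocol's methods, but protocol 10.3 and 10.3.3 were already descriptive. The mismatch lies within the protocol and is carried into the SAP.
- *That the analysis will never be done, or that precision cannot be known.* SAP 2 and SAP 11 allow further analyses and tables. A reader can also compute the interval and the t statistic from the reported n, mean and SD. The most that can be said is that neither is pre-specified.
- *That the other parts do this properly.* The Part C SAP also quotes power for a paired t-test (5.1) and then only summarizes its primary endpoint (7.2). The Part C and Part D SAPs offer 95% intervals for continuous variables only where appropriate. Part D does commit to intervals for hemoglobin response rates.

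It is also fair to say that a test adds little. Part B has no control group and entry requires hemoglobin of at most 10.5 g/dL, so rejecting zero change cannot separate a drug effect from regression to the mean. Power is already near its ceiling at 900 mg. In addition, the protocol's reference list cites a 2017 presentation of interim results from this study, so a test added now may follow sight of data.

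These points stand, and they make the interval more important than the p-value. They do not supply an analysis to match the power statement.

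**Conclusion.** The point holds as a mismatch between the sample-size text and the analysis plan. The stated power is numerically correct but corresponds to no pre-specified analysis, and the primary efficacy endpoint has no planned interval at either dose. This is worth correcting. It does not show that the study is too small at 900 mg.

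The size of the issue is the difference in precision: a half-width of roughly 0.25 to 0.38 g/dL at 900 mg against 0.55 to 0.63 g/dL at 1500 mg. These figures assume normally distributed changes, an observed SD equal to the planned 0.6 g/dL at both doses, and the group sizes shown. A different SD scales the half-widths in proportion.

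**What to change.** In Part A/B SAP 8.2.1, add a 95% confidence interval for mean Week 24 hemoglobin change at each dose level, and label the 1500 mg result as estimation only.

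Then reconcile the power text in protocol 10.1, the synopsis and SAP 6.1 in one of two ways:

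- report the paired t-test at 900 mg, two-sided 0.05, labelled post hoc if it is added after data have been reviewed; or
- restate the power figure as illustrative, describe Part B as descriptive, and give its expected precision.

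Either route should also settle the tension between the synopsis and the adequacy statement in protocol 10.1. An exact 95% interval for the proportion of hemoglobin responders is a useful option but is not needed to resolve this point.

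The cost is a few lines of text and trivial programming, with no change to enrollment or data collection.

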## **8.2.2. Analysis of the Secondary Efficacy Endpoints**

Change from baseline to each of the 4 week periods (Section 4, TSS definition) for the sickle cell disease severity measure (SCDSM) TSS, will be summarized. If SCDSM compliance is less than 75% for a 4-week period, the proportion will be considered missing.

Hematology parameters (reticulocyte count, indirect bilirubin, and LDH) and cerebral blood flow as measured by TAMM TCD velocity will be summarized at each visit for observed values and changes (absolute and percent) from baseline using appropriate descriptive statistics. If indirect bilirubin is missing and direct and total bilirubin are collected, indirect can be calculated as:

## **8.3. Safety**

All safety analyses will be conducted using the Safety Population.

### **8.3.1. Summary of Exposure**

Study drug administration in Part B will be summarized with number and percentage of participants receiving from 1 to the maximum number of doses by treatment group. Similarly, the duration of study drug exposure will be summarized with descriptive statistics.

The number and percentage of subjects who permanently discontinued study drug, and the reason for discontinuation (adverse event (AE) or other) will be summarized. The number and percentage of subjects who missed at least 1 dose of study drug or had at least 1 dose reduction will be summarized. The summary will include the number and percentage of subjects who had a dose reduction or dose interrupted due to an adverse event or other. Additionally, the number and percentage of subjects will be summarized in categories of number of interrupted doses and number of dose reductions.

### **8.3.2. Adverse Events**

Adverse events reported for participants participating in this study will be graded using the National Cancer Institute's (NCI) Common Terminology Criteria for Adverse Events (CTCAE), version 4.03. All AEs will be coded using the using MedDRA, version 20.0.

TEAE summary tables in both Part A and Part B will exclude sickle cell disease (SCD) related events defined as preferred terms of: combined acute chest syndrome and pneumonia, sickle cell anemia with crisis, osteonecrosis, and priapism. Additional select TEAE tables (Part B only) will summarize SCD related events which only include the preferred terms of acute chest syndrome and pneumonia (combined), sickle cell anemia with crisis, osteonecrosis, and priapism.

An overall summary will be presented which includes the number of TEAEs and the number and percentage of participants who experienced at least one TEAE. This summary will also include TEAEs Grade 3 or greater, TEAEs possibly/probably related to study drug, TEAEs leading to study drug reduction, TEAs leading to discontinuation of study drug, serious adverse events (SAEs), and deaths.

Additional summaries of TEAEs will be provided showing the number and percentage of participants who experienced at least one TEAE. These summaries will be presented by system organ class (SOC), preferred term (PT) and maximum severity. If a participant reports the same PT multiple times within the same SOC, that PT will only be counted once within that SOC for

that participant. As with the PT, if a participant reports multiple conditions within the same SOC, that SOC will only be counted once for that participant. In the summary, SOC will be listed in ascending alphabetical order; PTs will be listed in order of descending frequency for all participants within each SOC.

The occurrence of TEAEs possibly/probably related to GBT440 will be tabulated by SOC, PT and maximum severity. Serious adverse events will be presented by system organ class (SOC), preferred term (PT) and maximum severity.

Adverse events recorded in the eCRF which began prior to first dose of study drug will not be included in the summary tables.

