### 11.1. Tables Part A

Item	Title
Table 14.1.1.a	Demographics and Baseline Characteristics
Table 14.1.2.a	Baseline Sickle Cell Disease Characteristics
Table 14.1.3.a	Other Medical History
Table 14.1.4.a	Participant Follow-up and Termination from Study
Table 14.1.5.a	Concomitant Medications
Table 14.3.1.1.a	Overview of Treatment-Emergent Adverse Events and Serious Adverse Events
Table 14.3.1.2.a	Treatment-Emergent Adverse Events by System Organ Class, Preferred Term and Maximum Severity
Table 14.3.2.1.a	Summary of Hematology and Change from Baseline
Table 14.3.2.2.a	Summary of Serum Chemistry and Change from Baseline
Table 14.3.2.3.a	Summary of Liver Function Tests and Change from Baseline
Table 14.3.3.a	Corrected QT Interval (Fridericia) Maximum Post-Baseline and Maximum Increase from Baseline Categories

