## 11.2. Listings Part A

Item	Title
Listing 16.2.1.a	Eligibility and Enrollment for Screen Failures
Listing 16.2.2.a	Protocol Deviations for Safety Population
Listing 16.2.3.a	Demographics for Safety Population
Listing 16.2.4.a	Baseline Characteristics for Safety Population
Listing 16.2.5.a	Sickle Cell Disease History for Safety Population
Listing 16.2.6.a	Sickle Cell Disease Complications for Safety Population
Listing 16.2.7.a	Participant Follow-Up and Termination from Study for Safety Population
Listing 16.2.8.a	Prior and Concomitant Medications for Safety Population
Listing 16.2.9.a	Adverse Events for Safety Population
Listing 16.2.10.a	Study Drug Administration for Safety Population
Listing 16.2.11.1.a	Clinically Significant Laboratory Results for Safety Population
Listing 16.2.11.2.a	Coagulation Results for Safety Population
Listing 16.2.11.3.a	Urinalysis Results for Safety Population
Listing 16.2.11.4.a	Pregnancy Results for Safety Population
Listing 16.2.12.a	Vital Signs for Safety Population
Listing 16.2.13.a	Electrocardiogram for Safety Population
Listing 16.2.14.a	Physical Examinations for Safety Population

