### 11.3. Tables Part B

Item	Title
Table 14.1.1.b	Eligibility and Enrollment
Table 14.1.2.b	Demographics and Baseline Characteristics
Table 14.1.3.b	Baseline Sickle Cell Disease Characteristics
Table 14.1.4.b	Other Medical History
Table 14.1.5.b	Participant Follow-up and Termination from Study
Table 14.1.6.b	Concomitant Medications
Table 14.1.7.b	Study Drug Exposure
Table 14.2.1.1.b	Summary of Hemoglobin and Measures of Hemolysis
Table 14.2.1.2.b	Hemoglobin Responders
Table 14.2.2.b	Summary of TCD Velocity and Change from Baseline
Table 14.2.3.b	Summary of Sickle Cell Disease Measure Total Symptom Score and Change from Baseline
Table 14.3.1.1.b	Overview of Treatment-Emergent Adverse Events and Serious Adverse Events
Table 14.3.1.2.1.b	Treatment-Emergent Adverse Events by System Organ Class, Preferred Term and Maximum Severity
Table 14.3.1.2.2.b	SCD Related Treatment-Emergent Adverse Events by System Organ Class, Preferred Term and Maximum Severity
Table 14.3.1.3.1.b	Treatment-Emergent Adverse Events Related to Study Drug by System Organ Class, Preferred Term and Maximum Severity
Table 14.3.1.3.2.b	SCD Related Treatment-Emergent Adverse Events Related to Study Drug by System Organ Class, Preferred Term and Maximum Severity
Table 14.3.1.4.b	Treatment-Emergent Adverse Events by Preferred Term
Table 14.3.1.5.b	Treatment-Emergent Adverse Events Related to Study Drug by Preferred Term
Table 14.3.1.6.1.b	Serious Adverse Events by System Organ Class and Preferred Term and Maximum Severity
Table 14.3.1.6.2.b	SCD Related Serious Adverse Events by System Organ Class and Preferred Term and Maximum Severity
Table 14.3.2.1.b	Summary of Hematology and Change from Baseline

Item	Title
Table 14.3.2.2.b	Summary of Serum Chemistry and Change from Baseline
Table 14.3.2.3.b	Summary of Liver Function Tests and Change from Baseline
Table 14.3.2.4.b	Summary of Serum Erythropoietin and Change from Baseline
Table 14.3.3.b	Summary of Vital Sign and Weight
Table 14.3.4.1.b	Summary of Electrocardiograms
Table 14.3.4.2.b	Corrected QT Interval (Fridericia) Maximum Post-Baseline and Maximum Increase from Baseline Categories

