### 7.3.2. Adverse Events

Adverse events reported for subjects participating in this study will be graded using the National Cancer Institute's (NCI) Common Terminology Criteria for Adverse Events (CTCAE), version 4.03. All AEs will be coded using MedDRA (current version).

All adverse events summaries described below will be presented for both non-SCD and SCD-related TEAEs.

Non-SCD-related TEAE summary tables will exclude sickle cell disease (SCD) related events defined as preferred terms of: acute chest syndrome, pneumonia, pneumonia necrotising, sickle cell anemia with crisis, osteonecrosis, and priapism. Additional TEAE tables will summarize the aforementioned SCD related events.

Overall summaries will be presented which includes the number of TEAEs and the number and percentage of subjects who experienced at least one TEAE. The summaries will also include TEAEs Grade 3 or greater, TEAEs possibly/probably related to study drug, TEAEs leading to study drug reduction, TEAEs leading to study drug interruption, TEAEs leading to discontinuation of study drug, serious adverse events (SAEs) and SAEs possibly/probably related to study drug. TEAEs leading to deaths will be summarized together regardless if they are SCD-related as cause of death may include multiple TEAEs.

Additional summaries of TEAEs will be provided showing the number and percentage of subjects who experienced at least one TEAE. These summaries will be presented by system organ class (SOC), preferred term (PT) and maximum severity. If a subject reports the same PT multiple times within the same SOC, that PT will only be counted once within that SOC for that subject. As with the PT, if a subject reports multiple conditions within the same SOC, that SOC will only be counted once for that subject. In the summary, SOC will be listed in ascending alphabetical order; PTs will be listed in order of descending frequency for all subjects within each SOC.

The occurrence of TEAEs possibly/probably related to voxelotor will be tabulated by SOC, PT and maximum severity. Serious adverse events will be presented by system organ class (SOC), preferred term (PT) and maximum severity.

Grouped terms for rash and abdominal pain are summarized by PT.

Adverse events recorded in the eCRF which began prior to first dose of study drug will not be included in the TEAE summary tables.

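### The Part A/B SAP omits listed sickle-cell events from the main TEAE tables and, on a plain reading, from the overview; neither part has an all-event overview, and Part A only lists these events

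*SAP*

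**What the plan says.** Part A/B SAP, section 8.3.2:

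- The rule: "TEAE summary tables in both Part A and Part B will exclude sickle cell disease (SCD) related events".
- The excluded events form a closed list, "defined as preferred terms of: combined acute chest syndrome and pneumonia, sickle cell anemia with crisis, osteonecrosis, and priapism".
- Where they reappear: "Additional select TEAE tables (Part B only) will summarize SCD related events".
- The overview is described next. It counts TEAEs and participants with at least one, and has rows for Grade 3 or higher, drug-related events and dose reductions. It ends with "TEAs leading to discontinuation of study drug, serious adverse events (SAEs), and deaths". Nothing is said about whether the exclusion applies to these rows.

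Part A/B SAP, section 11:

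- Part A has two AE tables: Table 14.3.1.1.a, "Overview of Treatment-Emergent Adverse Events and Serious Adverse Events", and Table 14.3.1.2.a by system organ class (SOC), preferred term (PT) and severity. Its AE listing is 16.2.9.a, "Adverse Events for Safety Population", with no exclusion stated.
- Part B adds three SCD-related tables: 14.3.1.2.2.b, "SCD Related Treatment-Emergent Adverse Events by System Organ Class, Preferred Term and Maximum Severity", and the matching tables for drug-related TEAEs (14.3.1.3.2.b) and SAEs (14.3.1.6.2.b).

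Elsewhere:

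- Protocol section 10.3.2 tabulates participants reporting TEAEs, with serious TEAEs and TEAEs leading to discontinuation summarized separately. It excludes nothing.
- Part A/B SAP section 10 lists one change from the planned analyses, the dropped symptom-exacerbation endpoint.
- The Part C SAP (section 7.3.2) and Part D SAP (section 8.3.2) give every AE summary for both classes of event. On deaths, the Part C SAP says "TEAEs leading to deaths will be summarized together regardless if they are SCD-related"; the Part D SAP has the same rule.

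**The concern.** Safety and tolerability is a secondary objective of both parts, and TEAEs and SAEs are named safety endpoints. A reader goes to the overview first and takes its rows as totals. The planned titles of the overview and the main SOC/PT tables do not say that a class of events has been left out.

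The omitted terms matter in this disease. Parts A and B have no stroke or VOC incidence endpoint, which exists only for Parts C and D. Section 10 of the SAP also drops the symptom-exacerbation endpoint. Apart from the Part B diary symptom score, AE tables are the main place where crisis and acute chest syndrome on treatment would be summarized. If those events are absent from the overview, and from every Part A table, the report's total counts fall short of what the protocol promised.

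**Working it through.** The plan states no figure that bears on this point, so there is nothing to reproduce. The check compares texts and table lists, then works out what one participant is worth.

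**1. Planned AE outputs, SAP section 11**

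| Output | Part A main | Part A SCD-related | Part B main | Part B SCD-related |
|---|---|---|---|---|
| Overview | 14.3.1.1.a | none | 14.3.1.1.b | none |
| TEAEs by SOC, PT, severity | 14.3.1.2.a | none | 14.3.1.2.1.b | 14.3.1.2.2.b |
| Drug-related TEAEs by SOC, PT, severity | not planned | none | 14.3.1.3.1.b | 14.3.1.3.2.b |
| By PT only (all; drug-related) | not planned | none | 14.3.1.4.b; 14.3.1.5.b | none |
| SAEs by SOC, PT, severity | not planned | none | 14.3.1.6.1.b | 14.3.1.6.2.b |

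Part A therefore has no table for the excluded events. Part B has three, but no SCD-related or all-event overview.

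**2. Does the exclusion reach SAEs and deaths?** The overview is a TEAE summary table and section 8.3.2 gives no exception, so the plain reading is yes. The Part B numbering supports this for SAEs: 14.3.1.6.1.b is paired with an SCD-related 14.3.1.6.2.b, which suggests the first leaves those events out. For deaths there is only the general rule. In both cases this is inference, not an explicit statement.

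**3. Can the totals be rebuilt from the Part B tables?** For any row,

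N(any) = N(non-SCD) + N(SCD) − N(both).

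The split tables supply the first two terms where both versions exist. No planned table supplies N(both). All that follows is that N(any) lies between the larger of the two counts and their sum, capped at the group size. In Part A, N(SCD) is not tabulated either.

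**4. What one participant is worth.** A percentage in the overview falls by 1/n for each participant whose only event of that row's type is an excluded term. For the any-TEAE row, that participant must have no other TEAE. For the SAE row, it is enough that there is no other SAE. The count of TEAEs falls with every excluded event.

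- Part A overall, about 12 participants (protocol 3.1.1): 1/12 = 8.3 points.
- One Part A cohort, about 6; SAP section 8 presents select Part A summaries by age group: 1/6 = 16.7 points.
- Part B is presented by dose level. At the planned minimum of 6 on 1500 mg: 1/6 = 16.7 points. With the 7 and 25 participants mentioned in protocol 3.5.2: 1/7 = 14.3 and 1/25 = 4.0 points. Over all 36: 1/36 = 2.8 points.

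**5. How likely is an excluded event?** The documents give no rate. As an assumption, take 0.5 to 3 excluded-type events per participant-year, a constant rate and complete follow-up (protocol 3.2).

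- Part A: 12 × 15/365.25 = 0.49 person-years. Expected events are 0.25 to 1.48, and P(at least one) = 1 − exp(−expected) = 22% to 77%.
- Part B: 36 × 28 × 7/365.25 = 19.3 person-years. Expected events are 9.7 to 58.0. Expected participants with at least one are 36 × [1 − exp(−rate × 196/365.25)] = 8.5 to 28.8 of 36.

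These count participants with any excluded event. Those whose only TEAE is excluded will be fewer, so this is a ceiling on the effect on the any-TEAE row.

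**The case against.** The strongest reply is that the events are mostly reported, and that separating pre-specified disease-related terms is a transparent choice.

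- **Part B tables.** A reader might infer that the terms vanish from all TEAE tables. They do not: three planned tables show them with severity, relatedness and seriousness. This stands.
- **Reductions and discontinuations.** A reader might infer that an SCD-related discontinuation goes uncounted. Section 8.3.1 counts Part B discontinuations, reductions and interruptions due to AEs with no exclusion stated. This stands, although those counts could then disagree with the matching overview rows.
- **Part A.** Nothing is lost from the report. With about 12 children, a single dose and follow-up to Day 15, Listing 16.2.9.a can be read child by child. This stands, but a listing gives no summary count.
- **SAEs and deaths.** A reader might state as fact that these rows will be wrong. The text does not say so, and one clarifying sentence would settle it. Part B also has a listing of SAEs (16.2.8.2.b).
- **Scope of the list.** Only the named terms are removed. Sickle-cell events coded to other terms stay in the main tables.
- **Non-exhaustive list, superseding SAP.** Section 11 calls its tables key ones and allows additions. Section 2 lets the SAP replace the protocol's methods and says it serves an interim report. So an overview could still be added and the departure is permitted. Neither makes the overview planned or the departure declared.
- **Sponsor practice.** The Part C and D SAPs also keep the two classes apart and combine only deaths. They do not support rebuilding every SOC/PT table to include all TEAEs. They do give an overview for each class, which Parts A and B lack.

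**Conclusion.** The point holds in limited form. Followed as written, the main TEAE tables in Parts A and B omit the listed terms. On a plain reading so does the overview, including its Grade 3 or higher, SAE and death rows. Part B reports the events apart, in a form from which participant totals cannot be rebuilt; Part A only lists them. The protocol's TEAE tabulation has no such exclusion, and the SAP does not record the difference as a change.

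In Part A the size is 8.3 points per affected participant overall and 16.7 within a cohort of six, on the planned enrollment. Understatement arises only if excluded events occur, and for the any-TEAE row only if the participant has no other TEAE. The documents do not show that any count will in fact be wrong, or that deaths or SAEs are certain to be left out.

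**What to change.** In the Part A/B SAP:

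1. Add an all-TEAE overview for each part, with non-SCD and SCD-related columns beside the total. The split follows the Part C and D SAPs. The total column goes one step further and is needed because the two splits cannot be added.
2. State in section 8.3.2 that the SAE and death counts include SCD-related events.
3. Add an SCD-related TEAE table for Part A.
4. List the exclusion in section 10 as a change from protocol section 10.3.2.
5. Keep the separate non-SCD SOC/PT tables if wanted, with titles that say what they leave out.

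The cost is a few sentences and a few extra columns or tables from AE data already collected. Section 11 already allows additional tables.
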